#### **3.2. Study Design**

This study is a 2-arm, double-blind, randomized, placebo-controlled, parallel group, 3-site study designed to assess the effects of ASP8062 as compared with placebo on responses to *in vivo* alcohol cue exposure in the human laboratory setting. After signing informed consent, subjects will be screened for eligibility and have other baseline assessments. Screening is permitted over a 14-day period and most baseline assessments will be performed on the day of randomization. Assessments include alcohol breathalyzer test (before signing consent), medical history, physical examination, weight, vital signs, electrocardiogram (ECG), drinking history by the timeline follow-back (TLFB) method, Clinical Institute Withdrawal Assessment for Alcohol-revised (CIWA-AR), prior medication use, MINI neuropsychiatric interview, urine drug test, smoking quantity frequency and nicotine use interview, clinical laboratory tests including chemistry, hematology, medical urinalysis, alcohol craving responses during a baseline cue reactivity session, Columbia Suicide Severity Rating Scale (C-SSRS), drinking goal, Penn Alcohol Craving Scale (PACS), Pittsburgh Sleep Quality Index (PSQI), PROMIS Alcohol Negative Consequences short form, Profile of Moods State (POMS), Hyperkatifeia Scale and confirmation that subjects are treatment seeking and desire a reduction or cessation of drinking. Women of child-bearing potential will have a pregnancy test.

If eligible for the study, 60 subjects will be randomized using a stratified permuted block randomization procedure with “clinical site” as the stratification variable in an approximate 1:1 ratio (targeting 30 subjects per group) to receive either ASP8062 25 mg once daily or matched placebo for 6 weeks.

Subjects will be seen in the clinic at screening, at randomization and 5 other times during the study. A final follow-up telephone interview will occur ~2 weeks after the end of study in-clinic visit. Two cue reactivity sessions will be conducted. The first will be during screening (named pretreatment session) and the second will be after two weeks of investigational product

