**Table 1: Schedule of Assessments**

Study Phase	Screening	Treatment					End of Study a	Follow-up Call
Clinic Visit #	1	2	3	4	5	6	7	
Study Week (Days) b	-2 to -1 (-14 to -1)	1 (1 to 7)	2 (8 to 14)	3 (15 to 21)	4 (22 to 28)	5 (29 to 35)	7 (43 to 49)	9 (57 to 63)
Informed Consent	X							
Alcohol Breathalyzer	X	X	X	X	X	X	X	
Urine Drug Test c	X	X	X	X	X	X	X	
Locator Form	X	Update	Update	Update	Update	Update	Update	
Demographics	X							
Medical History	X	Update						
Physical Exam	X	Update						
Body Weight	X				X		X	
MINI	X							
C-SSRS		X	X	X	X	X	X	
Clinical Chemistry d	X				X		X	
Hematology e	X				X		X	
Medical Urinalysis f	X				X		X	
Pregnancy Test	X	X					X	
Birth control methods (all subjects)	X	Update	Update	Update	Update	Update	Update	

Study Phase	Screening	Treatment					End of Study a	Follow-up Call
Clinic Visit #	1	2	3	4	5	6	7	
Study Week (Days) b	-2 to -1 (-14 to -1)	1 (1 to 7)	2 (8 to 14)	3 (15 to 21)	4 (22 to 28)	5 (29 to 35)	7 (43 to 49)	9 (57 to 63)
Vital Signs g	X	X	X	X	X	X	X	
Eligibility Checklist	X	X						
Drinking Goal	X							
ECG	X				X		X	
Prior and Concomitant Meds	X	X	X	X	X	X	X	X
CIWA-AR	X	X	X	X	X	X	X	X
Screening Cue Reactivity Session: VAS Scales	X							
Randomization		X (Day 1)						
Blood for Drug Concentration					X		X	
Drug compliance/ accountability/ Review AiCure		Dispense Day 1	X	X	X	X	X	
AEs (open ended question)		X	X	X	X	X	X	X
Brief Telephone Interview h		once during the week	once during the week	As needed if the subject misses a clinic visit				
Take Control		X	X	X	X i	X	X	
Treatment Cue Reactivity Session: VAS Scales				X				

Study Phase	Screening	Treatment					End of Study a	Follow-up Call
Clinic Visit #	1	2	3	4	5	6	7	
Study Week (Days) b	-2 to -1 (-14 to -1)	1 (1 to 7)	2 (8 to 14)	3 (15 to 21)	4 (22 to 28)	5 (29 to 35)	7 (43 to 49)	9 (57 to 63)
TLFB	X	X	X	X	X	X	X	
Brief Drinking Questionnaire	as needed							
Exit Interview							X	
ACQ-SF-R	2X pre/post cue session			2X pre/post cue session				
PACS		X	X	X	X	X	X	
Cigarette smoking quantity/frequency and nicotine use		X				X	X	
PSQI		X				X	X	
POMS		X				X	X	
PROMIS Alcohol Negative Consequences		X					X	
Hyperkatifeia Scale		X						
Treatment Referral							X	
Follow-Up Telephone Interview								X
Final Subject Disposition								X

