## **9. STATISTICAL CONSIDERATIONS**

### **9.1. General Considerations**

For descriptive purposes, dichotomous and categorical variables will be presented as number of observations and percentages; continuous variables will be given as means, standard deviations (SD), median, minimum (min) and maximum(max). Statistical tests will be two-tailed at a 0.05 Type I error rate. P-values for the primary and secondary endpoints of  $< 0.05$  will be considered statistically significant. Endpoint data will also be screened for outliers and skewness.

Appropriate non-parametric tests will be used to compare treatment groups on continuous baseline characteristics that are not normally distributed. Continuous endpoint data that are not normally distributed will be transformed using either a square root, logarithmic, or inverse transformation, the selection of which is determined by skewness and kurtosis statistics with values closest to zero. Cohen's d will be used to calculate the effect size for means and Cohen's h or odds ratios will be used to calculate the effect size for proportions. Descriptive statistics – mean, SD, median, min and max – of all endpoint data will be provided for each assessment point or summarized at each week for drinking endpoints. All data will be presented in listings.

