### **9.7. Drug Exposure and Retention Analyses**

Drug exposure will be presented for each treatment group as the mean number of tablets taken by week and overall through AiCure during the entire treatment phase. The analysis will include the total number of tablets taken and the percent compliance. AiCure data will also be used for the number subjects receiving reminder intervention (phone calls, texts, or in person visits). Compliance will also be evaluated by determining the proportion of subjects who were prescribed ASP8062, reported taking ASP8062 (by AiCure assessment), and had a plasma sample with detectable ASP8062. Compliance by ASP8062 plasma levels will be reported as number and percentage of subjects with a level above the limit of detection at each time point. Descriptive statistics of plasma levels of ASP8062 and metabolites will also be provided. Samples with levels below of limit of quantitation will not be included in the summary statistics and the N will reflect the number with a detectable level at each timepoint.

The participation rate is the percentage of subjects with complete drinking data. Dropouts by week with cumulative percentages will be provided by treatment arm.

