**Table 10: AiCure Report of ASP8062 Versus ASP8062 Plasma Levels – mITT Subjects**

		AiCure Report Indicates Drug Taken (pill count must = 1, on the day before the blood sample was drawn)			
Timing	Plasma level Indicates Drug Taken a	Yes, n (%)	No, n (%)	p-value b	kappa c
Week 4	Yes				
	No				
Week 7	Yes				
	No				
Overall	Yes				
	No				

a Blood level of  $\geq$ xx ng/mL indicates drug taken

b Chi-square test for independence

c Kappa test for agreement

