**Table 12: Exit Interview – mITT Subjects**

	ASP8062	Placebo	Total	

Question	(N=xx)	(N=xx)	(N=xxx)	p-value 
Did you think you were receiving the study drug or the placebo?				0.xxx
Placebo	xx (xx.x%)	xx (xx.x%)	xx (xx.x%)	
Study Drug	xx (xx.x%)	xx (xx.x%)	xx (xx.x%)	
Don't know; No idea	xx (xx.x%)	xx (xx.x%)	xx (xx.x%)	
Refuse to answer	xx (xx.x%)	xx (xx.x%)	xx (xx.x%)	
What is your desire to please people?				0.xxx
More than average	xx (xx.x%)	xx (xx.x%)	xx (xx.x%)	
Average	xx (xx.x%)	xx (xx.x%)	xx (xx.x%)	
Less than average	xx (xx.x%)	xx (xx.x%)	xx (xx.x%)	
Refuse to answer	xx (xx.x%)	xx (xx.x%)	xx (xx.x%)	
Take the study drug again, for more than 6 weeks?				0.xxx
Yes	xx (xx.x%)	xx (xx.x%)	xx (xx.x%)	
No	xx (xx.x%)	xx (xx.x%)	xx (xx.x%)	
Refuse to answer	xx (xx.x%)	xx (xx.x%)	xx (xx.x%)	
Did you ever miss a dose of medication to avoid these effects?				
Yes	xx (xx.x%)	xx (xx.x%)	xx (xx.x%)	0.xxx
No	xx (xx.x%)	xx (xx.x%)	xx (xx.x%)	
Refuse to answer	xx (xx.x%)	xx (xx.x%)	xx (xx.x%)	
Did you use any other services during the study to help you reduce drinking?				0.xxx
Yes	xx (xx.x%)	xx (xx.x%)	xx (xx.x%)	
No	xx (xx.x%)	xx (xx.x%)	xx (xx.x%)	
Refuse to answer	xx (xx.x%)	xx (xx.x%)	xx (xx.x%)	

 p-value from chi-squared test (c) unless one of the cells expected is less than 5 then Fisher's exact test is used (f). Refuse to answer is not included in statistical test.

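### Tables 10 and 11 put a chi-square p-value for association beside kappa in a check of agreement, with cells too sparse for the test, no intervals and no stated rule for the Overall row

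*SAP*

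**What the plan says.** SAP section 9.7 describes the comparison as the proportion of subjects prescribed ASP8062 who "reported taking ASP8062 (by AiCure assessment), and had a plasma sample with detectable ASP8062". It names no test.

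The test appears only in the shell for Table 10. The shell crosses plasma Yes/No with AiCure Yes/No at Week 4, Week 7 and Overall, and shows n (%) in each cell. AiCure counts as Yes under the condition "pill count must = 1, on the day before the blood sample was drawn". Two statistics follow: a p-value footnoted as a "Chi-square test for independence" and a kappa footnoted as a "Kappa test for agreement". Table 11 repeats the layout in evaluable subjects, who by SAP section 4 took a tablet on at least 80% of days.

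Table 12, in the same SAP section, uses chi-square "unless one of the cells expected is less than 5", in which case it switches to Fisher's exact test. Table 10 has no such rule. No confidence interval is planned in Table 10, and nothing says how the Overall row combines the two visits.

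**The concern.** Section 9.7 asks whether plasma supports what AiCure records, which is a question of agreement. The chi-square null is that the two are unrelated. Rejecting it does not show that they agree, and failing to reject does not show that they disagree.

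The data are likely to be lopsided. The design is "targeting 30 subjects per group", and if most subjects take the drug the No cells will hold very few people. Chi-square is then unreliable or cannot be computed. Kappa, the planned agreement statistic, is weak in the same tables.

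AiCure is the source of the exposure and compliance tables (Tables 2 to 5), and Tables 10 and 11 are its check against plasma. At stake is how clearly that check can be read.

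**Working it through.** The plan gives no figure to reproduce: Tables 10 and 11 are empty shells. Inputs from the SAP are about 30 ASP8062 subjects (section 3.2), up to two samples each ("Blood for Drug Concentration" at Weeks 4 and 7 in the Schedule of Assessments), and two-sided alpha of 0.05 (section 9.1). Compliance, error rates and within-subject correlation are assumptions. Tables below are written [plasma Yes: AiCure Yes, AiCure No; plasma No: AiCure Yes, AiCure No].

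**1. Association against agreement.** For cells a, b, c, d, chi-square = n(ad − bc)² / product of the four margins.
- Perfect agreement [15, 0; 0, 15]: 30 × 225² / 15⁴ = 30.0, kappa +1.
- Perfect disagreement [0, 15; 15, 0]: 30 × (−225)² / 15⁴ = 30.0, kappa −1.

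The p-values are identical (p < 0.0001). Only kappa separates the two cases.

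**2. Expected counts.** When No is the rarer answer on both margins, the smallest expected count is (plasma No × AiCure No) / 30. Reaching 5 needs a product of at least 150, for example 13 × 13 = 169; 12 × 12 = 144 falls short. About 40% of subjects would have to be No on both measures. In simulations with 80% to 98% takers, the smallest expected count was below 5 in at least 98.6% of tables.

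**3. Tables where chi-square cannot be computed.** This happens when a margin is empty. Assume plasma sensitivity 0.99 and false positive 0.01, AiCure sensitivity 0.97 and false positive 0.02, with errors independent given true intake. Ignoring the negligible all-No case, P(not computable) = A³⁰ + P³⁰ − B³⁰, where A, P and B are the probabilities of AiCure Yes, plasma Yes and both Yes.
- 97% takers: A = 0.97 × 0.97 + 0.03 × 0.02 = 0.9415; P = 0.97 × 0.99 + 0.03 × 0.01 = 0.9606; B = 0.9315. Result: 0.164 + 0.299 − 0.119 = 0.344.
- 90% takers: A = 0.875; P = 0.892; B = 0.8643. Result: 0.018 + 0.032 − 0.013 = 0.038 from unrounded terms.

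The 97% figure matches simulation (0.345). With other assumed error rates (AiCure sensitivity 0.98 and no false AiCure reports; plasma sensitivity 0.95 to 0.98 and specificity 0.5 to 0.9), simulation gives 4–7% at 90% takers, 19–24% at 95% and 39–50% at 98%.

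**4. Kappa in the same tables.** Kappa = (po − pe) / (1 − pe).
- [30, 0; 0, 0]: po = pe = 1, so kappa is undefined.
- [29, 1; 0, 0]: po = 29/30 = 0.967 and pe = 30 × 29 / 900 = 0.967, so kappa is 0.00.
- [28, 1; 1, 0]: po = 0.933 and pe = (29 × 29 + 1) / 900 = 0.936, so kappa is −0.03. Chi-square is 30 / 841 = 0.036, p = 0.85.

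The test does not always fail: [28, 0; 0, 2] gives chi-square 30.0 and Fisher p = 0.0023.

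**5. Overall row, if the visits are simply pooled.** Suppose AiCure and plasma are unrelated, but each has correlation ρ between visits within a subject. The variance of the pooled association is inflated by about 1 + ρ², so the test rejects with probability P(|Z| > 1.96 / √(1 + ρ²)).

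| ρ | 1 + ρ² | Approximate rejection | Simulated range (positive rates 0.5 to 0.9) |
|---|---|---|---|
| 0 | 1.00 | 5.0% | 4.7–5.0% |
| 0.3 | 1.09 | 6.0% | 5.6–6.3% |
| 0.6 | 1.36 | 9.3% | 7.9–10.1% |
| 1 (values always repeat) | 2.00 | 16.6% | 12–18% |

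**The case against.** The strongest reply is that the SAP already plans the right kind of statistic. Kappa stands in the column beside the p-value, so a reader who infers that chi-square is the table's only check would be wrong. That stands, and it limits the criticism of the p-value to its being redundant and open to misreading. It does not rescue the table, because kappa fails in the same sparse layouts and no interval accompanies it.

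A reader might also infer that better agreement makes the test less likely to confirm AiCure. The documents give no basis for that, and the calculation contradicts it. At a fixed 97% takers, raising agreement from about 0.89 to 0.96 raises the chance of a significant result from about 0.44 to 0.56. At a fixed 80%, it rises from 0.98 to about 0.996. The loss comes from near-universal dosing.

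Nor do the documents say that the Overall row treats two samples from one subject as independent. The shell gives only a label. What stands is that the rule is missing and that simple pooling would have the effect shown.

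Near-universal Yes may not apply at Week 7. That visit is Days 43–49, and the shell for Table 2 gives a maximum of 42 tablets. A draw after Day 43 may have no scheduled dose the day before, so AiCure could read No whatever the earlier compliance.

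Finally, no decision rule uses this p-value, and the four cell counts let a reader work out percent agreement. Both points stand and keep this minor.

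**Conclusion.** The point holds as a minor improvement to a compliance table. The chi-square p-value answers a different question from section 9.7 and adds nothing useful to kappa. At about 30 subjects it almost always rests on an expected count below 5, without the fallback used two tables later. Where nearly everyone doses, it may not be computable (about 4% of tables at 90% takers and 35% at 97%, under the assumed error rates), and kappa is unstable or undefined too. Table 11 is the more exposed of the two because its population is selected for compliance.

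The Overall row needs a stated rule. Under simple pooling, the nominal 5% test would reject in about 6% (correlation 0.3), 8–10% (0.6) or 12–18% (values always repeat) of trials with no true relation.

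These sizes depend on compliance, error rates and correlations that the documents do not give, and the sparse-table figures may not describe Week 7. The consequence is confined to how well plasma is shown to support AiCure. The primary analysis is untouched.

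**What to change.** In Tables 10 and 11:
- Delete the chi-square p-value and its footnote.
- Report, separately for Week 4 and Week 7, the proportion of AiCure-Yes subjects with detectable plasma drug, the same proportion among AiCure-No subjects, and overall percent agreement, each with an exact 95% CI.
- Keep kappa as descriptive, with its CI, and print 'not estimable' when it cannot be computed.
- Give no inference in the Overall row, or use a CI clustered by subject, and state how the row is built.

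The cost is a change to two table shells and a sentence in section 9.7; no new data are needed. The downside is that the table no longer shows a p-value.

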**Table 11: AiCure Report of ASP8062 Versus ASP8062 Plasma Levels – Evaluable Subjects**

Repeat of Table 10 using evaluable subjects

**Table 12: Exit Interview – mITT Subjects**

	ASP8062	Placebo	Total	

Question	(N=xx)	(N=xx)	(N=xxx)	p-value 
Did you think you were receiving the study drug or the placebo?				0.xxx
Placebo	xx (xx.x%)	xx (xx.x%)	xx (xx.x%)	
Study Drug	xx (xx.x%)	xx (xx.x%)	xx (xx.x%)	
Don't know; No idea	xx (xx.x%)	xx (xx.x%)	xx (xx.x%)	
Refuse to answer	xx (xx.x%)	xx (xx.x%)	xx (xx.x%)	
What is your desire to please people?				0.xxx
More than average	xx (xx.x%)	xx (xx.x%)	xx (xx.x%)	
Average	xx (xx.x%)	xx (xx.x%)	xx (xx.x%)	
Less than average	xx (xx.x%)	xx (xx.x%)	xx (xx.x%)	
Refuse to answer	xx (xx.x%)	xx (xx.x%)	xx (xx.x%)	
Take the study drug again, for more than 6 weeks?				0.xxx
Yes	xx (xx.x%)	xx (xx.x%)	xx (xx.x%)	
No	xx (xx.x%)	xx (xx.x%)	xx (xx.x%)	
Refuse to answer	xx (xx.x%)	xx (xx.x%)	xx (xx.x%)	
Did you ever miss a dose of medication to avoid these effects?				
Yes	xx (xx.x%)	xx (xx.x%)	xx (xx.x%)	0.xxx
No	xx (xx.x%)	xx (xx.x%)	xx (xx.x%)	
Refuse to answer	xx (xx.x%)	xx (xx.x%)	xx (xx.x%)	
Did you use any other services during the study to help you reduce drinking?				0.xxx
Yes	xx (xx.x%)	xx (xx.x%)	xx (xx.x%)	
No	xx (xx.x%)	xx (xx.x%)	xx (xx.x%)	
Refuse to answer	xx (xx.x%)	xx (xx.x%)	xx (xx.x%)	

 p-value from chi-squared test (c) unless one of the cells expected is less than 5 then Fisher's exact test is used (f). Refuse to answer is not included in statistical test.

**Table 13: Exit Interview – Evaluable Subjects**

Same as Table 12

**Table 14: Dropouts by Treatment Group and Week – mITT Subjects**

	ASP8062 N=XX		Placebo N=XX		Total N=XX		
Study Week 	n	Cumulative n (%)	n	Cumulative n (%)	n	Cumulative n (%)	p-value 
Week 1	xx	xx (xx.x)	xx	xx (xx.x)	xx	xx (xx.x)	0.xxx
Week 2	xx	xx (xx.x)	xx	xx (xx.x)	xx	xx (xx.x)	0.xxx
Week 3	xx	xx (xx.x)	xx	xx (xx.x)	xx	xx (xx.x)	0.xxx
Week 4	xx	xx (xx.x)	xx	xx (xx.x)	xx	xx (xx.x)	0.xxx
Week 5	xx	xx (xx.x)	xx	xx (xx.x)	xx	xx (xx.x)	0.xxx
Week 6	xx	xx (xx.x)	xx	xx (xx.x)	xx	xx (xx.x)	0.xxx
Week 6	xx	xx (xx.x)	xx	xx (xx.x)	xx	xx (xx.x)	0.xxx

 Fisher's exact test Subjects are considered dropouts when they stop providing TLFB and other data. Subjects that discontinue study drug but provide data are not considered dropouts.**Table 15: Number and Percent of Subjects Using Brief Drinking Questions after Discontinuing TLFB – mITT Subjects**

	ASP8062	Placebo	Total	
Study Week	n (%)	n (%)	n (%)	p-value 
Week 3	xx (xx.x)	xx	xx.x	0.xxx
Week 4	xx	xx	xx.x	0.xxx
Week 5	xx	xx	xx.x	0.xxx
Week 6	xx	xx	xx.x	0.xxx
Week 6	xx	xx	xx.x	0.xxx
Overall	xx	xx	xx.x	0.xxx

Fisher's exact test is used because frequencies are expected to be low

Note only rows with values above 0 will be presented

### **12.1.2. Demographic and Baseline Characteristics**

**Table 16: Demographic Characteristics - mITT Subjects**

Characteristic	ASP8062	Placebo	Total	p-value 
Age (years)				0.xxx
N	xx	xx	xx	
Mean	xx.x	xx.x	xx.x	
SD 	xxx.xx	xxx.xx	xxx.xx	
Median	xx	xx	xx	
Min-Max	(xx-xx)	(xx-xx)	(xx-xx)	
Gender				0.xxx
N				
Male	xx (xx.x%)	xx (xx.x%)	xx (xx.x%)	
Female	xx (xx.x%)	xx (xx.x%)	xx (xx.x%)	
Race				0.xxx
N	xx	xx	xx	
White	xx (xx.x%)	xx (xx.x%)	xx (xx.x%)	
African-American or Black	xx (xx.x%)	xx (xx.x%)	xx (xx.x%)	
Asian	xx (xx.x%)	xx (xx.x%)	xx (xx.x%)	
Native Hawaiian or Other Pacific Islander	xx (xx.x%)	xx (xx.x%)	xx (xx.x%)	
American Indian or Alaskan Native	xx (xx.x%)	xx (xx.x%)	xx (xx.x%)	
Other	xx (xx.x%)	xx (xx.x%)	xx (xx.x%)	
Ethnicity				0.xxx
N	xx	xx	xx	
Hispanic or Latino	xx (xx.x%)	xx (xx.x%)	xx (xx.x%)	
Not Hispanic or Latino	xx (xx.x%)	xx (xx.x%)	xx (xx.x%)	

c = chi-squared test, f=Fisher's exact test, w=Wilcoxon signed rank test SD is standard deviation**Table 17: Demographic Characteristics – Evaluable Subjects**

Same as Table 16

**Table 18: Screening Cue Reactivity – mITT Subjects**

			ASP8062 N=xx	Placebo N=xx	Total N=xx	p-value
Cue	Question	Statistic				
Water	Craving Strength					0.xxx
		Mean (SD  )	xx.x (xx.xx)	xx.x (xx.xx)	xx.x (xx.xx)	
		Median	xx	xx	xx	
		Min-Max	(xx-xx)	(xx-xx)	(xx-xx)	
	Drinking makes things perfect					0.xxx
		Mean (SD)	xx.x (xx.xx)	xx.x (xx.xx)	xx.x (xx.xx)	
		Median	xx	xx	xx	
		Min-Max	(xx-xx)	(xx-xx)	(xx-xx)	
	Drink now					0.xxx
		Mean (SD)	xx.x (xx.xx)	xx.x (xx.xx)	xx.x (xx.xx)	

			ASP8062 N=xx	Placebo N=xx	Total N=xx	p-value 
		Median	xx	xx	xx	
		Min-Max	(xx-xx)	(xx-xx)	(xx-xx)	
	Turn down drink					0.xxx
		Mean (SD)	xx.x (xx.xx)	xx.x (xx.xx)	xx.x (xx.xx)	
		Median	xx	xx	xx	
		Min-Max	(xx-xx)	(xx-xx)	(xx-xx)	
	Average					0.xxx
		Mean (SD)	xx.x (xx.xx)	xx.x (xx.xx)	xx.x (xx.xx)	
		Median	xx	xx	xx	
		Min-Max	(xx-xx)	(xx-xx)	(xx-xx)	
Alcohol	Craving Strength					0.xxx
		Mean (SD)	xx.x (xx.xx)	xx.x (xx.xx)	xx.x (xx.xx)	
		Median	xx	xx	xx	
		Min-Max	(xx-xx)	(xx-xx)	(xx-xx)	

			ASP8062 N=xx	Placebo N=xx	Total N=xx	p-value 
	Drinking makes things perfect					0.xxx
		Mean (SD)	xx.x (xx.xx)	xx.x (xx.xx)	xx.x (xx.xx)	
		Median	xx	xx	xx	
		Min-Max	(xx-xx)	(xx-xx)	(xx-xx)	
	Drink now					0.xxx
		Mean (SD)	xx.x (xx.xx)	xx.x (xx.xx)	xx.x (xx.xx)	
		Median	xx	xx	xx	
		Min-Max	(xx-xx)	(xx-xx)	(xx-xx)	
	Turn down drink					0.xxx
		Mean (SD)	xx.x (xx.xx)	xx.x (xx.xx)	xx.x (xx.xx)	
		Median	xx	xx	xx	
		Min-Max	(xx-xx)	(xx-xx)	(xx-xx)	
	Average					0.xxx
		Mean (SD)	xx.x (xx.xx)	xx.x (xx.xx)	xx.x (xx.xx)	
		Median	xx	xx	xx	

			ASP8062 N=xx	Placebo N=xx	Total N=xx	p-value 
		Min-Max	(xx-xx)	(xx-xx)	(xx-xx)	
Alcohol - Water	Craving Strength					0.xxx
		Mean (SD)	xx.x (xx.xx)	xx.x (xx.xx)	xx.x (xx.xx)	
		Median	xx	xx	xx	
		Min-Max	(xx-xx)	(xx-xx)	(xx-xx)	
	Drinking makes things perfect					0.xxx
		Mean (SD)	xx.x (xx.xx)	xx.x (xx.xx)	xx.x (xx.xx)	
		Median	xx	xx	xx	
		Min-Max	(xx-xx)	(xx-xx)	(xx-xx)	
	Drink now					0.xxx
		Mean (SD)	xx.x (xx.xx)	xx.x (xx.xx)	xx.x (xx.xx)	
		Median	xx	xx	xx	
		Min-Max	(xx-xx)	(xx-xx)	(xx-xx)	
	Turn down drink					0.xxx

			ASP8062 N=xx	Placebo N=xx	Total N=xx	p-value
		Mean (SD)	xx.x (xx.xx)	xx.x (xx.xx)	xx.x (xx.xx)	
		Median	xx	xx	xx	
		Min-Max	(xx-xx)	(xx-xx)	(xx-xx)	
	Average					0.xxx
		Mean (SD)	xx.x (xx.xx)	xx.x (xx.xx)	xx.x (xx.xx)	
		Median	xx	xx	xx	
		Min-Max	(xx-xx)	(xx-xx)	(xx-xx)	

 t-test is used to examine balance across treatment groups

 SD is standard deviation

**Table 19: Screening Cue Reactivity – Evaluable Subjects**

Same as Table 18

**Table 20: Psychiatric Baseline Characteristics – mITT Subjects**

Characteristic	ASP8062 (N=xx)	Placebo (N=xx)	Total (N=xxx)
DSM-5 Disorders			
Depression	xx (xx.x%)	xx (xx.x%)	xx (xx.x%)
Suicidality	xx (xx.x%)	xx (xx.x%)	xx (xx.x%)
Manic	xx (xx.x%)	xx (xx.x%)	xx (xx.x%)
Hypomanic	xx (xx.x%)	xx (xx.x%)	xx (xx.x%)
Bipolar	xx (xx.x%)	xx (xx.x%)	xx (xx.x%)
Panic	xx (xx.x%)	xx (xx.x%)	xx (xx.x%)
Agoraphobia	xx (xx.x%)	xx (xx.x%)	xx (xx.x%)
Social Phobia	xx (xx.x%)	xx (xx.x%)	xx (xx.x%)
Obsessive Compulsive	xx (xx.x%)	xx (xx.x%)	xx (xx.x%)
Posttraumatic Stress	xx (xx.x%)	xx (xx.x%)	xx (xx.x%)
Substance Abuse	xx (xx.x%)	xx (xx.x%)	xx (xx.x%)
Psychotic	xx (xx.x%)	xx (xx.x%)	xx (xx.x%)
Mood	xx (xx.x%)	xx (xx.x%)	xx (xx.x%)
Anorexia	xx (xx.x%)	xx (xx.x%)	xx (xx.x%)
Bulimia	xx (xx.x%)	xx (xx.x%)	xx (xx.x%)
Binge-eating	xx (xx.x%)	xx (xx.x%)	xx (xx.x%)
Generalized Anxiety	xx (xx.x%)	xx (xx.x%)	xx (xx.x%)
Medical Organic	xx (xx.x%)	xx (xx.x%)	xx (xx.x%)
Antisocial Personality	xx (xx.x%)	xx (xx.x%)	xx (xx.x%)

